2.7.1 Full Analysis Set (FAS)

Study Period 1 Full analysis set (SP1 FAS): consists of all randomized subjects to whom IMP has been assigned. Following the intent-to-treat principle, subjects will be analyzed according to the treatment assigned at randomization. Subjects will be analyzed as per the actual true strata and not necessarily the assigned strata.

Study Period 2 Full analysis set (SP2 FAS): The SP2 FAS set includes all SP1 FAS patients entering Study Period 2. Patients will be analyzed according to the treatment group assigned in SP1 and per the actual true strata from the clinical database.

2.7.2 Per-protocol Set (PPS)

Week 12 Per-protocol analysis set (W12 PPS): consists of all patients in the SP1 FAS who complete Week 12/Visit 8 and do not have any major protocol deviations regarding the evaluation of the study's primary objective and have received at least 5 doses of IMP up to Week 10.

The major protocol deviations were defined in BDRM, refer to the BDRM minutes for the details (version final 1.0, dated 19-Mar-2018).

Study Period 1 Per-protocol set (SP1 PPS): consists of all patients in the W12 PPS who complete Week 24/Visit 14 and do not have any major protocol deviations regarding the evaluation of the study's key secondary objective and have received at least 5 doses of IMP from Week 12 to Week 22.

Study Period 2 Per-protocol set (SP2 PPS): consists of all patients in the SP1 PPS who complete the entire study (Week 48/Visit 16) and do not have any major protocol deviations during the entire study with regards to any efficacy assessment and have received at least 10 doses of IMP from Week 24 to Week 46.

As defined in the PPS definitions, in addition to major protocol deviations, patients who completed the required study visit but did not meet the study treatment compliance will also be excluded from the per-protocol sets:

- For W12 PPS, patients have to receive at least 5 doses of IMP up to Week 10. Patients should receive six doses of IMP from Baseline to Week 10 (i.e., Baseline, Week 2, 4, 6, 8, 10). A patient who completed Week 12 (i.e., Week 12 visit assessment is available in subject visit dataset) but missed 2 or more doses of IMP will be excluded from W12 PPS.
- For SP1 PPS, patients have to receive at least 5 doses of IMP from Week 12 to Week 22. Patients should receive six doses of IMP from Week 12 to Week 22 (i.e., Week 12, 14, 16, 18, 20, 22). A patient who completed Study Period 1 (based on disposition dataset) but missed 2 or more doses of IMP will be excluded from SP1 PPS.
- For SP2 PPS, patients have to receive at least 10 doses of IMP from Week 24 to Week 46. Patients should self-administrate twelve doses of IMP biweekly from Week 24 to Week 46 (i.e., the EPOCH variable equals to "Treatment Period 2" in study drug exposure dataset). A patient who completed the Study Period 2 (based on disposition dataset) but missed 3 or more doses of IMP will be excluded from SP2 PPS.

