### **5.5.6 Rescue medication**

As all other RA treatments are prohibited per protocol, therefore a use of rescue medication for RA would lead to discontinuation of the patient from study treatment and withdrawal from the study. If any rescue medication for RA is used, this must be recorded in the (e)CRF.

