**Table 5-2      Prohibited Medication**

Medication	Washout period before randomization (baseline)
Other biological DMARDs (for example alefacept, briakinumab, efalizumab, ustekinumab, anakinra, abatacept)	6 months
Other synthetic DMARDs	
Cyclosporine	4 weeks
Cyclophosphamide	6 months
Leflunomide	8 weeks, unless a cholestyramine wash-out has been performed
Hydroxychloroquine, chloroquine, azathioprine	at least 5 half-lives to account for the pharmacokinetic profile of these products
Other systemic non-biologic DMARDs	4 weeks
Any investigational treatment or participation in any interventional trial	6 months or 5 half-lives (whichever is longer)
Live vaccinations ‡	3 months
Intra articular corticosteroids	4 weeks

‡If the patient received a live vaccination during the study, the patient must discontinue study treatment.

No other medications for treatment of RA are allowed to be used routinely during the study. Treatments displayed in [Table 5-2](#) could confound the efficacy and may affect safety, and are **NOT** allowed after randomization (baseline; Visit 2) for any indication. If the use of these treatments is required, then the patient should **NOT** be randomized into the study.

If the medication listed in [Table 5-2](#) was used during the study, it must be discontinued if the subject wishes to continue in the study. If the medication is not discontinued, subject will be withdrawn. If the patient received a live vaccination during the study, the patient must discontinue study treatment.

The investigator should instruct the patient to notify the study site about any new treatments that he/she takes after the start of study. All treatments and significant non-drug therapies administered after the patient entered the study must be listed on the Concomitant medications eCRF or the Procedures and Significant non-drug therapies eCRF.

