## **5.5.9      Study drug discontinuation and premature patient withdrawal**

### **Study drug discontinuation**

Patients may voluntarily discontinue study treatment for any reason at any time. The investigator should discontinue study treatment for a given patient if, based on benefit/risk assessment, he/she believes that continuation would not be favorable to the patient's well-being or if a patient did not improve (did not achieve the treatment target) or the disease activity deteriorated compared to previous DAS28-CRP score.

Study treatment must be discontinued under the following circumstances:

- Withdrawal of informed consent

- Violation of methods of contraception as described in Section [6.5.7](#)
- Emergence of the following AEs:
  - Any severe or serious AE that is not compatible with the administration of study drug
  - In case of a serious infection or sepsis
  - Severe heart failure (NYHA class III or IV), or other severe, uncontrolled cardiovascular disease
  - Uncontrolled hypersensitivity to study medication
  - Any persisting laboratory abnormalities that in the judgement of the investigator, taking into consideration the patient's overall status, prevents the patient from continuing participation in the study
  - Hepatitis B virus (HBV) infection. Should a patient develop HBV infection during the study, the study medication should be discontinued and should not be re-started, even after the infection is controlled or resolved. MTX should also be discontinued until the HBV infection is controlled or resolved.
  - Occurrence of any signs or symptoms of tuberculosis or suspicion of tuberculosis (per the investigator's discretion) during study course will lead to discontinuation of study drug and the patient will be withdrawn from the study
  - Malignancy, except for basal cell carcinoma
- Pregnancy
- Use of the prohibited medications as described in Section [5.5.8](#)
- Any other protocol deviation that results in a significant risk to the patient's safety
- Non-responders at Week 24
- Emergency unblinding

The date and primary reason for stopping study treatment should be recorded in the eCRF (e.g. Study Drug Discontinuation Form).

See Section [6](#) for the required assessments of these patients after study drug discontinuation.

The investigator must also notify the IRT system of the study drug discontinuation.

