### **Premature patient withdrawal**

Patients may voluntarily withdraw from the study for any reason at any time. They may be considered withdrawn if they:

- State an intention to withdraw
- Fail to return for visits and after several attempts by the site personnel to reach this patients
- Become lost to follow up for any other reason

If such withdrawal occurs for any reason the investigator must determine the primary reason for a patient's premature withdrawal and record this information on the Study completion eCRF page. The investigator must also notify the IRT system of the premature withdrawal.

Patients who prematurely withdraw from the study, should be scheduled for a final assessment visit (as defined for EoS/ Visit 16), as described in [Table 6-1](#). For patients whose status is unclear because they fail to appear for study visits without stating an intention to withdraw, the investigator should show "due diligence" by contacting the patient, family or family physician as agreed in the informed consent and by documenting in the source documents steps taken to contact the patient, e.g. dates of telephone calls, registered letters, other.

If the investigator decides that a patient is not responding adequately to the study medication, patient should be withdrawn and may receive thereafter any anti-rheumatic treatments at the discretion of the investigator. Patient should undergo a final assessment visit which should be performed prior to treatment with the new anti-rheumatic therapy, and will then be withdrawn from the study. Lack of study drug efficacy should be stated on the study completion eCRF page for these patients.

Patients who are prematurely withdrawn from the study will not be replaced by newly enrolled patients.

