#### **9.4.4 Supportive analyses**

The same MMRM analysis as used for analysis of the primary endpoint will be conducted as a sensitivity analysis using the SP1 FAS.

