2.7 Definitions of analysis sets

The following analysis sets will be used for this analysis.

The primary endpoint analysis will be based on W12 PPS, and will be repeated on SP1 FAS as sensitivity analysis.

The key secondary endpoint analysis will be based on SP1 PPS, and will be repeated on SP1 FAS as sensitivity analysis.

The analyses of Study Period 1 data will be based on SP1 FAS, SP1 SAF, SP1 PPS.

The analyses of Study Period 2 data will be based on SP2 FAS, SP2 SAF, SP2 PPS.

In addition to the study protocol defined objectives, the entire study data (i.e., from the randomization up to Week 48) will also be analyzed based on SP1 FAS, SP1 SAF, SP2 PPS.

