4.5 Analysis of the primary endpoint

The change from baseline in DAS28-CRP at week 12 will be analyzed using the method described in Section 2.4.1.

The primary analysis will be performed on the Per-protocol set (W12 PPS) which is the most conservative approach to show equivalent efficacy as this analysis set is the “cleanest” sample of the study population to identify differences, if there are any.

The MMRM will include the patient into the analysis as long as there is at least one non-missing DAS28-CRP change from baseline value.

The stratification factors in the primary analysis model will use the data from clinical database as it is most correct data and there are known incorrect stratification assignments in IRT data.

Table 4-1 MMRM Analysis SAS® Code

```
/* Save the LS Means and the differences into datasets */
ods output Diff = Diff LSMeans = LSMeans;
proc mixed data=DATASETNAME method=reml covtest;
  class VISIT TREATMENT USUBJID REGION RA_MED BODY_WEIGHT;
  model CHG = BSL VISIT TREATMENT VISIT*TREATMENT REGION
    RA_MED BODY_WEIGHT / solution ddfm=KR;
  repeated VISIT / type=un subject=USUBJID;
  lsmeans TREATMENT / diff CL;           /* Overall treatment effect */
  lsmeans VISIT*TREATMENT / diff CL;   /* treatment effect per visit */
run;
```

Note: names in capitals are only placeholders for the real dataset or variable names; select the model parameter estimations at visit Week 12 only from the SAS output datasets.

Sensitivity analysis of primary endpoint:

- Repeat the primary analysis based on SP1 FAS
- Repeat the primary analysis using IRT stratification data
- Repeat the primary analysis using the statistical model with treatment as fixed effect and body weight as continuous covariate (i.e., other stratifications like region and prior therapy will be excluded from the model)
- Repeat the primary analysis using the statistical model with treatment as fixed effect only

- Repeat the primary analysis by ADA status up to Week 12 (Positive/Negative)

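### Week 12 equivalence is decided by W12 PPS alone, which drops most early withdrawals for inadequate response; whether this favours equivalence is not fixed, so the planned SP1 FAS analysis should share the decision

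*SAP*

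**What the plan says.** **Which set decides.** SAP 2.7: "The primary endpoint analysis will be based on W12 PPS, and will be repeated on SP1 FAS as sensitivity analysis". Protocol 9.4.2 also makes W12 PPS the primary set, and Protocol 9.4.4 gives the full set a supporting role: "The same MMRM analysis as used for analysis of the primary endpoint will be conducted as a sensitivity analysis using the SP1 FAS". Neither document says that the SP1 FAS interval must meet the margin.

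**Who is in it.** Under SAP 2.7.2, W12 PPS "consists of all patients in the SP1 FAS who complete Week 12/Visit 8 and do not have any major protocol deviations" affecting the primary objective. At least 5 of the 6 doses due by Week 10 are also required.

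**Who leaves early.** Protocol 5.5.9 states: "If the investigator decides that a patient is not responding adequately to the study medication, patient should be withdrawn". It also has the investigator stop study treatment "if a patient did not improve (did not achieve the treatment target) or the disease activity deteriorated compared to previous DAS28-CRP score". Protocol 5.5.6 says that "a use of rescue medication for RA would lead to discontinuation of the patient from study treatment and withdrawal from the study". The rescue route is less certain, because Protocol 5.5.8 says of a Table 5-2 medication used on study that "it must be discontinued if the subject wishes to continue in the study". Those passages must be reconciled, but the point here does not depend on how.

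**The reason given.** SAP 4.5 calls the choice of W12 PPS "the most conservative approach to show equivalent efficacy", on the ground that it is the cleanest sample in which to see a difference.

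**The concern.** Membership of the deciding set depends partly on the outcome being compared. A patient withdrawn for inadequate response at Week 6, say, does not complete Week 12 and leaves W12 PPS entirely. The Week 2 and Week 4 DAS28-CRP values go too, although the planned MMRM accepts any patient with one post-baseline change. The way back in is narrow: an exit visit assigned to Week 12 (SAP 2.1.2 and 4.1.4) in a patient with at least 5 doses.

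If one product is truly less effective and both arms withdraw only clearly poor responders, the weaker arm loses more of its worst outcomes and the completers look more alike. In an equivalence trial that favours success. As written, equivalence could be declared on W12 PPS while the SP1 FAS interval crosses 0.6, and no rule covers that conflict.

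**Working it through.** **Inputs from the documents** (SAP 2.4.1, 2.5.1): margin ±0.6, SD 1.30, 154 randomized and 123 evaluable per arm, 20% loss from the per-protocol set, 5% or 2.5% per side.

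**Assumptions** (not in the documents): comparator mean changes of -0.8/-1.3/-2.0 at Weeks 2/4/12; GP2017 worse by 0.24/0.39/0.60; SD 1.3 at each visit; correlations 0.7 (Weeks 2-4), 0.7 (4-12) and 0.49 (2-12); 8% further random loss in the simulations.

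**Step 1. The plan's power.** SE = 1.30 × sqrt(2/123) = 0.1658, and 0.6/SE = 3.619. Power = 2Φ(3.619 - 1.645) - 1 = 95.2% with the 90% CI, and 2Φ(3.619 - 1.960) - 1 = 90.3% with the 95% CI. Also 123/0.8 = 153.75, or 154. The stated 95% and 90% reproduce.

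**Step 2. Effect of selection.** Suppose a patient whose trigger value exceeds a cut-off c is withdrawn with probability q. Let z = (c - arm mean of the trigger)/1.3 and p = 1 - Φ(z), and let r be the correlation of the trigger with the Week 12 change. The lack-of-efficacy (LoE) withdrawal rate is q × p. The mean Week 12 change among those who stay falls by r × 1.3 × q × φ(z)/(1 - q × p).

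**Step 3. Worked case.** The trigger is the observed Week 4 change above 0, with q = 0.5 and r = 0.7.
- GP2017: z = 0.91/1.3 = 0.7, p = 0.242, LoE 12.1%. Fall = 0.91 × 0.5 × 0.3123/0.879 = 0.162.
- Humira: z = 1.3/1.3 = 1.0, p = 0.159, LoE 7.9%. Fall = 0.91 × 0.5 × 0.2420/0.921 = 0.120.
- W12 PPS difference = 0.600 - 0.162 + 0.120 = 0.558.

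**Step 4. Range at a true difference of 0.6.** Estimates use the Step 2 formula. False-equivalence rates are simulated (20,000 trials per scenario), except the last row, which uses the normal approximation.

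| Trigger for withdrawal | q | LoE, GP2017/Humira | W12 PPS estimate | False equivalence, 90%/95% CI |
|---|---|---|---|---|
| Observed Week 4 change > 0 | 0.10 | 2.4%/1.6% | 0.593 | 5.5%/2.9% |
| same | 0.25 | 6.0%/4.0% | 0.582 | 6.3%/3.4% |
| same | 0.50 | 12.1%/7.9% | 0.558 | 8.6%/4.5% |
| Unseen Week 12 change > -0.6 | 0.25 | 6.7%/3.5% | 0.560 | 8.3%/4.8% |
| same | 0.50 | 13.5%/7.0% | 0.508 | 15.0%/9.1% |
| Unseen Week 12 change > -2.0 | 0.10 | 6.8%/5.0% | 0.605 | not run |
| Unseen Week 12 change > -2.5 | 0.10 | 8.0%/6.5% | 0.612 | not run |
| Observed Week 4 change > -1.2 | 0.10 | 5.9%/4.7% | 0.600 | not run |
| Observed Week 4 change > -2.0 | 0.10 | 8.0%/7.0% | 0.606 | 4.6%/2.3% |

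The last four rows show why direction is not automatic. φ(z) peaks at z = 0, so once the cut-off lies near or below the arm means, the weaker arm's fall is no longer clearly the larger. The 15%/9% figure is not a mathematical ceiling. If every patient beyond the cut-off left and 5% did so overall, the same kind of calculation gives 0.491 and 17.9%/10.9%.

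**Step 5. No true difference.** The simulated mean estimate stayed within 0.002 of zero, so there is no bias.

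**Step 6. What SP1 FAS adds.** When withdrawal follows observed Week 4 values (missing at random, MAR), the SP1 FAS MMRM averages 0.60 with false equivalence of 4.9-5.1%/2.3-2.6%. Requiring both sets gives 4.2-4.5%/2.0-2.2%. When withdrawal follows the unseen Week 12 value (missing not at random, MNAR), protection is partial. In the two MNAR cases with cut-off -0.6, FAS averages 0.578 and 0.549, and requiring both sets gives 5.9%/3.0% and 8.9%/4.8%. If 25%, 50% or 100% of the LoE withdrawals in the second case had an exit value counted as Week 12 in FAS only, the two-set figure falls to 7.3%/3.7%, 6.0%/3.0% or 4.6%/2.2%.

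**The case against.** **The choice is deliberate, and FAS is already reported.** This stands. The same MMRM on SP1 FAS is prespecified, SAP 4.2 counts discontinuations before Week 12 and summarises SP1 reasons, and Protocol 5.5.9 asks for a final assessment before new therapy. But reporting a second analysis does not say what follows if it fails the margin, and none of the other sensitivity analyses in SAP 4.5 addresses informative withdrawal.

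**Early efficacy exits may be few.** This also stands. Protocol 3.2 places the assessment of improvement at three months, DAS28 is scheduled only at Weeks 2 and 4 before Week 12, and the explicit non-responder stop is at Week 24. Neither document gives an early LoE rate. The 20% is total loss from the per-protocol set (SAP 2.5.1) or total dropout (Protocol section 4). The extreme case uses about half of it, (13.5% + 7.0%)/2 = 10.25%, and puts the true difference exactly on the margin.

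**Other per-protocol exclusions can act the other way.** Patients with missed doses or major deviations may dilute a real difference in FAS. That is the sound part of the SAP 4.5 rationale, and the calculations above do not model it.

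**The direction is not guaranteed.** This is correct. Protocol 5.5.9 is worded widely enough to reach patients who simply miss a treatment target, and with such cut-offs the shift disappears or reverses slightly at ordinary withdrawal rates.

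**Conclusion.** The point holds in a conditional form. W12 PPS alone decides Week 12 equivalence and omits most early withdrawals for inadequate response, with their Week 2 and 4 data. If the products differ and withdrawal is concentrated among clearly poor responders, false equivalence exceeds 5%/2.5%. In the models used here it ranges from near nominal to about 8.5%/4.5% under MAR, and reaches about 15%/9% only in an extreme MNAR case. The means, correlations, cut-offs and withdrawal probabilities are all assumptions.

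A reader might infer that the W12 PPS estimate is always pulled toward zero, or that the trial's error rate is known to be inflated. The documents support neither. They give no withdrawal rate or cut-off, the shift can reverse, and the opposing effect of the other exclusions is unquantified. What they do show is that the SAP 4.5 description of W12 PPS as most conservative is not true in general. This is an inexpensive improvement to the decision rule. The sample size calculation is not in error.

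**What to change.** 1. State that, at each confidence level, Week 12 equivalence is concluded only if the W12 PPS interval and the already planned SP1 FAS MMRM interval both lie within [-0.6, 0.6]. This changes the protocol's decision rule, so it belongs in SAP section 3 (Changes to planned analyses) or in an amendment of Protocol 9.4.2 and 9.4.4, with matching text in SAP 2.7 and 4.5. SAP 2.4 reports the protocol's method and is not the place for it. The rule must be fixed before database lock and unblinding.
2. In SAP 4.5, replace "the most conservative approach to show equivalent efficacy" with wording limited to missed doses and protocol deviations.
3. Add a tipping-point (missing-not-at-random) analysis on SP1 FAS to the SAP 4.5 sensitivity list, because the two-set rule restores nominal error only under MAR.
4. Restate power in SAP 2.5.1 for the two-set rule.

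Optional: cross-tabulate discontinuation reason by before/after Week 12 and arm in SAP 4.2. In SAP 4.1.4, say whether an exit visit outside the Week 12 window enters the SP1 FAS model as Week 12, since 2.1.2 and 4.1.4 can be read differently.

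**Cost.** With a true difference of 0 and 20% random loss, simulated power for W12 PPS alone is 95.0% (90% CI) and 89.8-90.1% (95% CI). For both sets it is 94.5-94.7% and 88.9-89.5%. If the 20% is all dropout, it is 94.5%/88.9%, up to about one point below the stated 95%/90%. Beyond that the cost is one extra analysis and a documented change from the protocol. The W12 PPS definition and all clinical withdrawal rules stay as they are.

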2.7.3 Safety set (SAF)

Study Period 1 Safety set (SP1 SAF): consists of all subjects who received at least one dose of IMP, whether randomized or not. Subjects will be analyzed according to the treatment received.

Study Period 2 Safety set (SP2 SAF): The SP2 SAF set includes all SP1 SAF patients entering Study Period 2 who received at least one dose of IMP in Study Period 2.

3 Changes to planned analyses

Based on the study protocol Section 2.2, the efficacy evaluation of Study Period 2 includes calculating the changes from Week 24 at Week 48 for the following variables: DAS28-CRP, DAS28-ESR, HAQ-DI score, and FACIT fatigue score. In addition to changes from Week 24 at Week 48, the changes from baseline (i.e., randomization) at all applicable Study Period 2 visits will also be calculated and analyzed for above variables.

In addition to the study protocol defined objectives for SP1 and SP2 separately, the entire study data (i.e., from the randomization up to Week 48) will also be analyzed.

The SAP section “Power for analysis of key secondary endpoint”, more detailed information than in the study protocol are provided.

The protocol specifies no imputation for missing components of the DAS28-CRP score, because it was assumed that joint surgery would not occur. In accordance with general practice, the joints which not assessable throughout the study will be considered as not having tenderness or swelling (see Section 2.3.1.1).

4 Statistical analyses

